12.2.4	Electronic and central data validation	53
12.3	Monitoring.....	53
12.4	Audits and Inspections	53
12.5	Confidentiality, Data Protection.....	53
12.6	Storage of biological material and related health data.....	53
13.	PUBLICATION AND DISSEMINATION POLICY.....	54
14.	FUNDING AND SUPPORT.....	54
14.1	Funding	54
14.2	Other Support	54
15.	INSURANCE.....	54
16.	REFERENCES.....	55
17.	APPENDICES.....	59
17.1	Certifications and specifications of e-liquids	59

STUDY SYNOPSIS

Sponsor / Sponsor-Investigator	[name]. med [name] (Sponsor-Investigator)
Study Title:	Efficacy, Safety and Toxicology of Electronic Nicotine Delivery Systems as an aid for smoking cessation: The ESTxENDS multicentre randomized controlled trial
Short Title / Study ID:	ESTxENDS
Protocol Version and Date:	2.0, 12.03.2018
Trial registration:	Clinicaltrials.gov, Swiss national clinical trials portal (SNCTP)
Study category and Rationale	Other clinical trial, risk category B. ENDS and e-liquids are considered alimentary good in Switzerland and thereby regulated by the law on alimentary good. Sale and use of ENDS and e-liquids exempt from nicotine is permitted in Switzerland. Swiss residents can order nicotine-containing e-liquids from online stores abroad for personal use. Direct sale of nicotine-containing e-liquids is forbidden in Switzerland. Because Swiss law considers ENDS and e-liquids as alimentary good, and not as medicinal products or medical devices, Swissmedic has waived approval and surveillance. We will follow the rules set by the Federal Office of Public Health (FOPH) and the Federal Food Safety and Veterinary Office (FSVA) for the import of nicotine-containing e-liquids and have participants order the liquids from abroad and have the e-liquids sent directly to their home.
Clinical Phase:	n.a.
Background and Rationale:	Cigarette smoking is the leading cause of preventable death in Switzerland. Recently, electronic nicotine delivery systems (ENDS or vaporizers, also called e-cigarettes) have become popular with smokers who want to switch from tobacco cigarettes to ENDS to reduce their exposure to toxic compounds or to stop smoking. Only two rigorous RCTs have been published so far. They have promising, yet inconclusive results, as they were based on small samples. The safety and potential adverse effects of ENDS are also largely unknown. While the aerosol the users inhale appears safe in laboratory conditions, the difference in exposure to toxins (such as measures of exposure to organic compounds) and effect of toxins on the body (measures of oxidative stress) between smokers who quit (with or without ENDS) and those who use ENDS for a long time have not yet been assessed in an RCT.
Objective(s):	Test ENDS on: 1) the efficacy for cigarette smoking cessation and reducing the number of cigarettes smoked over 6 months of follow-up; 2) the safety of ENDS on adverse events; 3) the effect of ENDS on reducing exposure to inhaled toxic compounds; 4) the effect of ENDS on health-related outcomes (clinical outcomes: respiratory symptoms; surrogate outcomes: oxidative stress, risk factors for heart disease).


Outcome(s):
	
 - The primary outcome will be the continuous smoking abstinence from target quit date to the 6-month follow-up visit, ascertained by self-report (self-report of no smoking from target quit date) and confirmed by exhaled CO level (CO<10 ppm) and urinary level of cotinine, anabasine (<3 ng/ml) and NNAL (10 pg/mg creat). - Secondary smoking cessation outcome will alternate methods to define the smoking cessation outcome: as the primary outcome, but allowing up to 5 cigarettes in total and a 2-week 'grace period' after the target quit date, self-reported 7-day point prevalence abstinence, all confirmed by the exhaled CO level, urinary level of cotinine and anabasine, and change in the self-reported number of cigarettes smoked per day (CPD) with 50% reduction in CPD from baseline to follow-up considered as successful reduction. - Concentrations of urinary tobacco-specific nitrosamines (TSNAs), volatile organic compounds (VOCs), aldehydes and polycyclic aromatic hydrocarbons (PAHs) for all participants. Participants will complete detailed questionnaire to account for other sources of contaminants. - Respiratory symptoms (self-report) - Oxidative stress assessed by 8-OHdG and 8-isoprostane concentrations in both exhaled breath condensate (EBC) and urine; - Cardiovascular risk factors (CVRF) assessed by HDL- and LDL-cholesterol, HbA1c, creatinine and glucose concentrations, blood pressure levels, waist circumference, and body mass index. - Adverse events (AEs), serious adverse events (SAEs) following international standards. - Mood, anxiety and sleep quality (Self report)

Study design:
	
Open-label randomized controlled trial


Inclusion / Exclusion criteria:
	
Inclusion criteria:
 
 - Informed Consent as documented by signature - Persons aged 18 or older - Currently smoking 5 or more cigarettes a day for at least 12 months - Willing to try to quit smoking within the next 3 months, - Persons providing a valid phone number, a valid email address and/or a valid postal address. 
Exclusion criteria:
 
 - Known hypersensitivity or allergy to contents of the e-liquid - Participation in another study with investigational drug within the 30 days preceding the baseline visit and during the present study where interactions are to be expected - Women who are pregnant or breast feeding - Intention to become pregnant during the course of the study - Persons having used ENDS regularly in the 3 months preceding the baseline visit - Persons having used nicotine replacement therapy (NRT) or other drug therapy helping smokers quit (varenicline, bupropion) within the 3 months preceding the baseline visit - Plans to move out of the country within the next 6 months, or cannot attend the 6- month follow-up visit for any reason - Cannot understand instructions delivered in person or by phone, or otherwise unable to participate in study procedures

Measurements and procedures:	
An overview on the study measurements and procedures is provided in the study schedules. The main measurements and procedures are the following:
 
We plan to include 1172 smokers in a pragmatic RCT that will add ENDS to smoking cessation counselling (SCC), and compare ENDS to SCC alone. Participants in the intervention arm will receive free ENDS and nicotine-containing e-liquids ad libitum. Participants in both arms will receive SCC in four sessions over two months over the phone, and be allowed to use NRTs and other smoking cessation help in parallel. At baseline and 6-month follow-up, we will distribute questionnaires and perform a battery of clinical tests, including tests for cardiovascular risk factors (blood pressure, lipids, HbA1c, creatinine and glucose; body mass index), determine urinary biomarkers for tobacco-specific nitrosamines (TSNAs), nicotine metabolites (nicotine, cotinine, anabasine), metabolites of polycyclic aromatic hydrocarbons (PAHs) (1-hydroxypyrene, 1-and 2-naphthol)), volatile organic compounds (VOCs) and oxidative stress markers in urine and exhaled breath condensates (EBC) (8-hydroxy-2'-deoxyguanosine and 8- iso-prostaglandin F22α).

Study Product / Intervention:	
Participants in the intervention arm will receive free ENDS and nicotine-containing e-liquids ad libitum; plus smoking cessation counseling (SCC). Participants will be allowed to choose the flavor and nicotine concentration of the e-liquids. Use of ENDS during the 6 months will be ad libitum and will be monitored by use of e-liquids in ml. Study nurses will provide the technical support for the use of ENDS and schedule a phone call on the participant's target quit date. On the target quit date as well as at week 1, 2, 4 and 8 after target quit date, study nurses will call participants for SCC and further technical support (see below).

Control Intervention:	
Participants in the control group will receive SCC (standard of care). Nurses will be trained to deliver standardized SCC. SCC will be provided in person at the first clinical visit (baseline visit) and then over the phone at the target quit date) and again at week 1, 2, 4 and 8 after target quit date.

Number of Participants with Rationale:	
Number of participants projected for the entire study: 1172; Intervention group: 586, control group: 586. Rationale see in section "Statistical considerations".

Study Duration:	
3 years

Study Schedule:	
First participant in: 04/18 Last participant out: 03/20

Investigator(s):	
[name]. med [name] Berner Institut für Hausarztmedizin (BIHAM) Universität Bern [name] [name] [contact] [contact]
 
PD [name] Institut Universitaire de Santé au Travail University of Lausanne and Geneva [name] Biopôle 1 [name] [contact] [contact]
 
[name]. med. [name] Policlinique Médicale Universitaire Université de Lausanne [name] [name] [contact] [contact]
 
[name]. med. [name] Klinik und Poliklinik für Allgemeine Innere Medizin Inselspital [name] [name] [contact] [contact]
 
PD Dr. med. [name] Département de médecine interne HUG Clinique de Médecine II [name] [name] [contact] [contact]

Study Centre(s):	Three sites in Switzerland including University Hospitals Bern, Geneva, and Lausanne.

Statistical Considerations:

Sample size:

Based on the results of a systematic review and meta-analysis of previous trials, we expect a RR of smoking cessation of 1.6; based on our experience with RCTs in the setting of smokers willing to quit and contacting health professionals to seek help receiving SCC alone, we expect a 12% quit rate in the control group and thus 19% in the intervention group (ENDS + SCC) (7% absolute difference in abstinence rate). With a two-sided alpha of 0.05 and a power of 90%, we will include a minimum 557 smokers per group, for a total of 1114 smokers, to find a significant difference in quit rates. Previous experience suggests we should assume a 5% loss to follow-up, so we will increase our sample size by 5% (59 smokers). We will thus recruit 1172 smokers. We will consider participants lost to follow-up to be continuing smokers, and our primary analysis will be intention-to-treat. Though participants in the control group will not be actively provided with ENDS and asked not to use ENDS during the first 6 months of the study, we expect 5% will still purchase ENDS on their own, and thus cross over from the control to the intervention group. The sample size of the entire trial is based on the primary outcome; the power to find a statistically significant difference for secondary outcomes is limited to the total number of participants.

Efficacy analysis:

To answer the primary research question, we will compare the rates of quitting among smokers randomized to ENDS vs. those receiving usual care, on an intention-to-treat basis. Continuous smoking cessation from target quit date will be the main outcome, confirmed by biomarkers of exposure (exhaled carbon monoxide (CO), urinary cotinine, anabasine and NNAL).[1] We will calculate quit rates, relative risks (RR), and absolute risks for ENDS +SCC (intervention group) compared to SCC alone (control group). We will further compare groups using multivariate regression models adjusting for appropriate co-variables. Participants lost during follow-up will be categorized as ongoing smokers in the intention-to-treat analysis. We intend to obtain full follow-up data on all randomized participants (see Follow-up and Retention). Participants who stopped smoking, and who are ongoing ENDS users, will be considered quitters. We will present per-protocol analyses in sensitivity analyses given that participants in the control group might start using ENDS in the first six months.

We will repeat these calculations for the secondary smoking cessation outcomes such as alternate definitions of the outcome of having quit smoking: a.) <5 cig from target quit date and b.) 7-days point abstinence (no cigarettes within the 7 days before outcome assessment)).

To test the effect of ENDS on reducing the number of cigarettes smoked per day, we will define a binary predictor of $\geq 50\%$ smoking reduction from baseline to follow-up smoking and repeat the analyses for the main outcome of quitting. We will also use joint multivariate random-effects (JMRE) models allowing to model CPD and smoking cessation. In addition, we will use mixed linear effect model to analyze the change in CPD modelled as a continuous outcome over time.

We will compare the proportion of adverse events and serious adverse events between groups using recommended methods. For the measures of changes in measures of urinary biomarkers, exhaled breath measures, CVRFs and respiratory symptoms from baseline to the 6-months visit, we will first compare the changes in these measures between the intervention and control group using two-sample t-tests or Wilcoxon rank-sum test, whenever appropriate. We will then fit univariate and multivariate mixed linear effect models. We will use multivariate linear and multinomial logistic regression models to compare groups according to their exposure to tobacco smoking and ENDS.

GCP Statement:	This study will be conducted in compliance with the protocol, the current version of the Declaration of Helsinki, the ICH-GCP or ISO EN 14155 (as far as applicable) as well as all national legal and regulatory requirements.
-----------------------	---

STUDY SUMMARY IN LOCAL LANGUAGE

Hintergrund

Rauchen ist die häufigste vermeidbare Todesursache in der Schweiz. Immer mehr Raucher, die sich den giftigen Substanzen des Tabakrauchs weniger aussetzen möchten oder einen Tabakrauchstopp anstreben, steigen ganz oder teilweise auf tabakfreie Vaporizer (e-Zigaretten, engl. auch electronic nicotine delivery systems, ENDS) um, mit denen nikotinhaltige Flüssigkeit (e-Liquids) verdampft werden. Momentan ist jedoch noch umstritten, ob ENDS als Unterstützung zur Rauchentwöhnung wirklich generell von Nutzen sind und welche Risiken der Konsum von ENDS birgt.

Ziele des Projekts

Im Rahmen einer kontrollierten, randomisierten klinischen Studie werden wir 1172 RaucherInnen, die entweder eine Rauchstoppberatung alleine oder in Kombination mit ENDS erhalten werden über jeweils 6 Monate begleiten. Wir werden die Effektivität von ENDS zur Tabakentwöhnung prüfen, indem wir bestimmen, ob die Anzahl gerauchter Zigaretten mit Hilfe der ENDS gesenkt werden kann bzw. ein totaler Rauchstopp erreicht wird. Gleichzeitig werden allfällige Nebenwirkungen erfasst, um die Sicherheit der ENDS zu beurteilen. Weiter wird erhoben, inwiefern sich die Schadstoffexposition beim Konsum von ENDS im Vergleich zum Tabakrauchen ändert, und ob sich gesundheitliche Aspekte wie Atemwegsbeschwerden sowie Blut- und Urinwerte, beispielsweise bezüglich oxidativem Stress oder kardiovaskulären Risikofaktoren, verbessern.

Bedeutung

Bisher wurden zwei klinische Studien zu Rauchentwöhnung mit ENDS publiziert. Bezüglich Nutzen der ENDS zur Rauchentwöhnung sind die Resultate zwar vielversprechend, aber noch nicht genug aussagekräftig, da die Anzahl untersuchter Personen gering war. Daten zu Sicherheit und Schadstoffen der ENDS liegen noch kaum vor. Die Positionen der Gesundheitsfachleute und Entscheidungsträger der Politik sind kontrovers: Einige vertreten die Ansicht, dass ENDS als sichere Alternative zum konventionellen Tabakrauchen aktiv angepriesen werden sollten; andere sind der Meinung, dass man von deren Gebrauch abraten sollte, da sie gesundheitsschädlich sein könnten und nicht zum Rauchstopp beitragen. Die Resultate unserer Studie sollen demnach Konsumenten, Gesundheitsfachpersonen und Politikern unabhängige und fundierte Information zu Sicherheit und Schadstoffen von ENDS liefern und zu der Entscheidung beitragen, ob ENDS aktiv als Alternative zum Tabakrauchen angepriesen werden sollen. Die Studie soll zeigen, ob sich ENDS zur Rauchentwöhnung eignen und damit Raucher-assoziierte Erkrankungen und Folgekosten für das Gesundheitswesen reduziert werden und langfristig etliche Leben gerettet werden könnten, die durch Tabakrauchen gefährdet sind.

ABBREVIATIONS

AE	Adverse Event
ASR	Annual Safety Report
CA	Competent Authority (e.g. Swissmedic)
CEC	Competent Ethics Committee
CRF	Case Report Form
CO	Carbon monoxide
CPD	Cigarettes per day
eCRF	Electronic Case Report Form
CTCAE	Common terminology criteria for adverse events
CVRF	Cardiovascular risk factors
DSUR	Development safety update report
EBC	Exhaled breath condensates
ENDS	Electronic nicotine delivery devices
GCP	Good Clinical Practice
IB	Investigator's Brochure
HbA1c	Glycated hemoglobin
HDL-cholesterol	High-density lipoprotein cholesterol
Ho	Null hypothesis
H1	Alternative hypothesis
HRA	Federal Act on Research involving Human Beings
IMP	Investigational Medicinal Product
IIT	Investigator-initiated Trial
ISO	International Organisation for Standardisation
ITT	Intention to treat
LDL- Cholesterol	Low-density lipoprotein cholesterol
MD	Medical device
NRT	Nicotine replacement therapy
NNAL	4-(methylnitrosamino)-1-(3-pyridyl)-1-butanol
NNK	Nicotine-derived nitrosamine ketone (4-(methylnitrosamino)-1-(3-pyridyl)-1-butanone)
NNN	N'-nitrosonornicotine
PAH	Polycyclic Aromatic Hydrocarbons
PI	Principal Investigator
RCT	Randomized Clinical Trial
SCC	Smoking Cessation Counselling
SDV	Source Data Verification
SOP	Standard Operating Procedure
SPC	Summary of product characteristics
SUSAR	Suspected Unexpected Serious Adverse Reaction

TMF Trial Master File
TNSAs Tobacco-specific nitrosamines
VOCs Volatile organic compounds

STUDY SCHEDULE

Procedure	Screening ①	Baseline visit	Day 0 ①	Week 1 ①	Week 2 ①	Week 4 ①	Week 8 ①	Outcome Visit Month 6
Visit timing Day 0 is target quit date (TQD)	-x to -8 days	-7 days	Day 0 (TQD)	+ 7 days	+14 days	+ 28 days	+ 56 days	+ 180 days
Visit window				±2 days	±3 days	±4 days	±1 week	-4/+12 weeks
ENROLLMENT								
Eligibility screen	x	x						
Explanation of project and protocol	x	x						
Send informed consent	x							
Sign informed consent		x						
Randomization to ENDS (E) or control		x						
Set target quit date (TQD)	x							
ASSESSMENT								
Demographics	x	x						
Medical History		x						
Physical activity		x						x
Smoking history	x	x						
Nicotine dependence		x						x
Withdrawal symptoms		x						x
Environmental pollution (e.g. second hand smoke)		x						x
Alcohol and illegal drug use		x						x
Anxiety		x						x
Depression symptoms		x						x
Sleep quality		x						x
Quality of life		x						x
Women: pregnancy test		x						
INTERVENTION								
ENDS distribution		E						
E-liquid order by participants		E			E	E	E	
E-liquid sent to their homes		E			E	E	E	

ENDS instruction		E						
ENDS technical support			E	E	E	E	E	
Structured smoking cessation counselling		x	x	x	x	x	x	
OUTCOME MARKERS								
Tobacco use (questionnaires)	x	x	x	x	x	x	x	x
Estimated ENDS use (ml e-liquids used)			E	E	E	E	E	E
Exhaled CO		x						x
Urinary nicotine metabolites		x						x
Urinary metabolite of Nitrosamines (TSNAs)		x						x
Adverse events, serious adverse events		x	x	x	x	x	x	x
VOC, aldehyde and PAH metabolites in urine		x						x
Oxidative stress markers in urine		x						x
Oxidative stress in exhaled breath (Lausanne site only)		x						x
Blood pressure, heart rate, height, weight (BMI), waist circumference		x						x
Blood lipids, HbA1c, creatinine & glucose		x						x
Respiratory symptoms		x						x

E: ENDS group only; C: Control group only

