Study Centre(s):	Five sites in Switzerland including University Hospitals Bern, Geneva, Lausanne, Zürich and St. Gallen.

Statistical Considerations:
	
Sample size:
 
Based on the results of a systematic review and meta-analysis of previous trials, we expect a RR of smoking cessation of 1.6; based on our experience with RCTs in the setting of smokers willing to quit and contacting health care professionals to seek help receiving SOC alone, we expect a 12% quit rate in the control group and thus 19% in the intervention group (ENDS + SOC) (7% absolute difference in abstinence rate). With a two-sided alpha of 0.05 and a power of 90%, we will include a minimum 557 smokers per group, for a total of 1114 smokers, to find a significant difference in quit rates. Previous experience suggests we should assume a 5% loss to follow-up, so we will increase our sample size by 5% (59 smokers). We will thus recruit 1172 smokers. We will consider participants lost to follow-up to be continuing smokers, and our primary analysis will be intention-to-treat. Though participants in the control group will not be actively provided with ENDS and asked not to use ENDS during the first 6 months of the study, we expect that 5% will still purchase ENDS on their own. The sample size of the entire trial is based on the primary outcome; the power to find a statistically significant difference for secondary outcomes is limited to the total number of participants.
 
Efficacy analysis:
 
To answer the primary research question, we will compare the rates of quitting among smokers randomized to ENDS vs. those receiving SOC, on an intention-to-treat basis. Continuous smoking cessation from target quit date will be the main outcome, confirmed by urinary anabasin levels.¹ We will calculate quit rates, relative risks (RR), and absolute risks for ENDS + SOC (intervention group) compared to SOC alone (control group). We will further compare groups using multivariate regression models adjusting for appropriate co-variables. Participants lost during follow-up will be categorized as ongoing smokers in the intention-to-treat analysis. We intend to obtain full follow-up data on all randomized participants (see Follow-up and Retention). Participants who stopped smoking, and who are ongoing ENDS users, will be considered quitters. We will also present per-protocol analyses given that some participants in the control group might start using ENDS in the first six months.
 
We will apply the same data analysis methods for the secondary smoking cessation outcomes such as: a.) <5 cig from target quit date and b.) 7-days point prevalence abstinence (no cigarettes within the 7 days before outcome assessment)).
 
To test the effect of ENDS on reducing the number of cigarettes smoked per day, we will define a binary predictor of $\geq 50\%$ cigarettes per day of reduction (cpd) from baseline to follow-up. We will also use joint multivariate random-effects (JMRE) models allowing to model CPD and smoking cessation. In addition, we will use mixed linear effect model to analyze the change in CPD modelled as a continuous outcome over time.
 
We will compare the proportion of adverse events and serious adverse events between groups using recommended methods. As to changes in measures of urinary biomarkers, exhaled breath measures, CVRFs and respiratory symptoms from baseline to the 6-, 12- and 24-months visit, we will first compare the changes in these measures between the intervention and control group using two-sample t-tests or Wilcoxon rank-sum test, whenever appropriate. We will then fit univariate and multivariate mixed linear effect models. We will use multivariate linear and multinomial logistic regression models to compare groups according to their exposure to tobacco smoking and ENDS.

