5. STUDY OUTCOMES

5.1 Primary Outcome

The primary outcome for the main analysis at 6-months follow-up will be the continuous smoking abstinence from target quit date (TQD) to the 6-month follow-up visit, ascertained by self-report (self-report of no smoking from target quit date) and confirmed by urinary level of anabasine (<3 ng/ml).^{1, 34, 35} If anabasine is missing, validation will be done by exhaled carbon monoxide (CO) (<10 ppm).

The primary outcome for the extended follow-ups at 12- and 24-months will be the self-reported 7-day point prevalence abstinence (not having smoked cigarettes within the preceding week), again confirmed by urinary level of anabasine (<3 ng/ml). If anabasine is missing, validation by exhaled carbon monoxide (CO) (<10 ppm).

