6.1 Outcome definitions

Primary outcome: The primary outcome will be the continuous cigarette smoking abstinence from target quit date to the 6-month follow-up visit, ascertained by self-report at the 6-month follow-up exam (self-report of no smoking from target quit date) and confirmed by urinary level of anabasine (<3 ng/ml). If anabasine is missing, validation by exhaled carbon monoxide (CO). The outcome is a binary outcome.

Core secondary outcomes:

- Secondary smoking cessation outcomes to the 6-month follow-up visit:
 - Continuous smoking abstinence. Self-report of having smoked no cigarettes from TQD, validated by urinary levels of NNAL (4-(methylnitrosamino)-1-(3-pyridyl)-1-butanol). If NNAL is missing, validation by urinary levels of anabasine or exhaled CO.
 - Self-reported smoking abstinence allowing a 2-week 'grace period' after the TQD
 - Validated smoking abstinence allowing a 2-week 'grace period' after the TQD, validated by urinary levels of anabasine. If anabasine is missing validation by exhaled CO.
 - Validated smoking abstinence allowing a 2-week 'grace period' after the TQD, validated by urinary levels of NNAL. If NNAL is missing, validation by urinary levels of anabasine or exhaled CO.
 - Self-reported smoking abstinence allowing up to 5 cigarettes in total after the TQD.
 - Validated smoking abstinence allowing up to 5 cigarettes in total after the TQD, validated by urinary levels of anabasine. If anabasine is missing validation by exhaled CO.
 - Validated smoking abstinence allowing up to 5 cigarettes in total after the TQD, validated by urinary levels of NNAL. If NNAL is missing, validation by urinary levels of anabasine or exhaled carbon monoxide (CO).
 - Self-reported 7-day point prevalence abstinence at 6 months, Self-report of having smoked no cigarettes in the past seven days.
 - Validated 7-day point prevalence abstinence. Confirmation of having smoked no cigarettes in the past seven days, validated by urinary levels of anabasine. If anabasine is missing validation by exhaled carbon monoxide (CO).
 - Validated 7-day point prevalence abstinence. Confirmation of having smoked no cigarettes in the past seven days, validated by urinary levels of NNAL. If NNAL is missing, validation by urinary levels of anabasine or exhaled carbon monoxide (CO).

CTU Bern	SAP for: ESTxENDS	Version: 4.02.0	
CTU Bern	Template: Statistical Analysis Plan (SAP)	Version: 03	
	Code: CS_STA_TEM-11	Valid from: 28.02.2019 to 06.2023	Page 18 of 27

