6.2 Derivation of Outcomes

Comments to secondary smoking cessation outcomes:

- Smoking is allowed during the grace period.
- The number of cigarettes smoked since the last visit is recorded as a categorical variable (1-5 cigarettes, >5 cigarettes). If the participant smoked more than once a day cigarettes in the last 7 days, the value is recorded as numeric variable. For secondary smoking cessation outcomes, we will assume the median value for the categorical variable. I.e. if a subject records 2 times to smoke 1-5 cigarettes, we assume him to be over the limit of 5 cigarettes.

Table 3: Derivation of primary and secondary outcomes.

Outcome	eCRF sheet	Variable	Variable type	Derivation	Outcome type
Primary: continuous smoking abstinence from target quit date to the 6-month follow-up visit AND	cig_ecig	quit_smoke_again	Binary: No, Yes	{ [Week 1/2/4/8, and month 6] quit_smoke_again == No AND quit_tobacco_inhale ==	Binary
		quit_tobacco_inhale	Binary: No, Yes		
	cig_ecig_6m	quit_smoke_again	Binary: No, Yes		
		quit_tobacco_inhale	Binary: No, Yes		

CTU Bern	SAP for: ESTxENDS	Version: 1-02.0
-----------------	-------------------	---------------------------------

CTU Bern	Template: Statistical Analysis Plan (SAP)	Version: 03
	Code: CS_STA_TEM-11	Valid from: 28-02-2019 to 05-06-2023

urinary level of anabasine (<3 ng/ml) OR	to be defined	to be defined	to be defined	No} AND {x < 3 if x!=missing, vs_co2_level<10 if x==missing & vs_co2_level ==missing}
CO level	vital_6m	vs_co2_level	Continuous	
Secondary outcomes				
continuous smoking abstinence from target quit date to the 6-month follow-up visit AND	Cig_ecig, cig_ecig_6m	quit_smoke_again, quit_tobacco_inhale	Binary: No, Yes, Binary:No, Yes	{[Week 1/2/4/8, and month 6] quit_smoke_again == No AND quit_tobacco_inhale == No} AND
urinary level of NNAL (<10 pg/ml creat) OR	To be defined	To be defined	To be defined	{y < 10 if y!=missing, x<3 if y==missing & x!=missing, vs_co2_level<10 if y==missing & x==miss- ing & vs_co2_level!=missing }
urinary level of anabasine (<3 ng/ml) OR	To be defined	To be defined	To be defined	
CO level	Vital, Vital_6m	vs_co2_level	continuous	
Continuous smoke abstinence allowing a 2-week grace period after TQD	cig_ecig / cig_ecig_6m	quit_smoke_again quit_tobacco_inhale	Binary: No, Yes	[Week 4, Week 8, and 6 months] sum(quit_smoke_again == No) >= 2 AND sum(quit_tobacco_in- hale == No) >= 2

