urinary level of NNAL (<10 pg/ml creat) OR	To be defined	To be defined	To be defined	{ y < 10 if y!=missing, x<3 if y==missing & x!=missing, vs_co2_level<10 if y==missing & x==missing & vs_co2_level!=missing }	
urinary level of anabasine (<3 ng/ml) OR	To be defined	To be defined	To be defined		
CO level	Vital, Vital_6m	vs_co2_level	continuous		
Self-reported 7-day point prevalence abstinence at 6 months	cig_ecig_6m	quit_smoke_again, quit_smoke_7days	Binary: No, Yes	quit_smoke_again == No AND quit_smoke_7days == No	Binary
Self-reported 7-day point prevalence abstinence at 6 months AND	cig_ecig_6m	quit_smoke_again, quit_smoke_7days	Binary: No, Yes Binary: No, Yes	{ quit_smoke_again == No AND quit_smoke_7days == No} AND { x < 3 if x!=missing, vs_co2_level<10 if x==missing & vs_co2_level ==missing}	Binary
urinary level of anabasine (<3 ng/ml) OR	To be defined	To be defined	To be defined		
CO level	Vital, Vital_6m	vs_co2_level	continuous		
Self-reported 7-day point prevalence abstinence AND	cig_ecig_6m	quit_smoke_again, quit_smoke_7days	Binary: No, Yes	{quit_smoke_again == No AND quit_smoke_7days == No} AND	Binary
urinary level of NNAL (<10 pg/ml creat) OR	To be defined	To be defined	To be defined	{y < 10 if y!=missing, x<3 if y==missing & x!=missing, vs_co2_level<10 if	
urinary level of anabasine (<3 ng/ml) OR	To be defined	To be defined	To be defined		

CTU Bern	SAP for: ESTxENDS	Version: 4.02.0
----------	-------------------	---------------------------------

CTU Bern	Template: Statistical Analysis Plan (SAP)	Version: 03
	Code: CS_STA_TEM-11	Valid from: 28.02.2019 5.6.2023

CO level	Vital, Vital_6m	vs_co2_level	continuous	y==missing & x==missing & vs_co2_level!=missing}	
Number of cigarettes smoked per day (CPD)	cig_ecig / cig_ecig_6m	quit_more1perday	continuous (number of cigarettes per day in the last 7 days)	[BL, TQD, phone visits and 6-month visit] quit_more1perday	Continuous
Change in the self-reported number of cigarettes smoked per day in the last 7 days	cig_ecig / cig_ecig_6m	quit_more1perday	continuous (number of cigarettes per day in the last 7 days)	(quit_more1perday[month 6] / quit_more1perday[day 0]) >= 0.5 IF [month 6]{contact_estab_yn == Yes AND quit_smoke_again == Yes AND quit_smoke_7days == Yes AND quit_smoke_nperday == ">=1x/Tag"} ELSE TRUE	Binary
CAT	cat / cat_6m	q1 to q8	radio (0 to 5)	sum(q1 to q8)[cat_6m] – sum(q1 to q8)[cat]	continuous (score scale 0-40, difference can be 0-40 as well)

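### SAP Table 3 fails the primary outcome on an inhaled-tobacco item that section 6.1 does not mention and that the up-to-5-cigarette and 7-day rows omit without explanation

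*Supplement*

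**What the plan says.** **Outcome text.** SAP 2.0 section 6.1 reads: "The primary outcome will be the continuous cigarette smoking abstinence from target quit date to the 6-month follow-up visit". It words the secondary cessation outcomes in terms of cigarettes too. Protocol 9.0 section 5.1 describes the 6-month primary outcome as "ascertained by self-report (self-report of no smoking from target quit date" and does not say which products count as smoking. For months 12 and 24 the same section uses 7-day abstinence, "not having smoked cigarettes within the preceding week), again confirmed by urinary level of anabasine (<3 ng/ml". The synopsis gives the 7-day outcome as "7-days point abstinence (no cigarettes within the 7 days before outcome assessment" in protocol 2.0 and as "7-days point prevalence abstinence (no cigarettes within the 7 days before outcome assessment" in protocol 9.0.

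**Code.** In SAP 2.0 section 6.2, Table 3, the primary row needs "quit_smoke_again == No AND quit_tobacco_inhale" both equal to No at weeks 1, 2, 4 and 8 and month 6, plus anabasine below 3 ng/ml, or CO if anabasine is missing. The self-report part of the 7-day rows is "quit_smoke_again == No AND quit_smoke_7days == No". The up-to-5 rows take their self-report part from `quit_smoke_n` alone.

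Neither document shows the eCRF question behind `quit_tobacco_inhale` or explains why some rows use it and others do not.

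**The concern.** Two things do not match. The primary outcome's text covers cigarettes, while its code also covers inhaled tobacco. And the outcomes meant to support the primary result drop a condition that the primary imposes.

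Continuous and point-prevalence abstinence may differ by design, because they cover different periods. That does not explain the up-to-5 rows, which run over the same period as the primary outcome. The protocol 9.0 synopsis introduces them as the primary outcome with an allowance for a few cigarettes and a grace period. On that description the cigarette count and the timing are relaxed, and nothing else.

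At stake is how the secondary results read. They should show whether the primary finding survives a more lenient count or a shorter window. As coded, a difference could also come from a change in what counts as smoking.

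**Working it through.** The plan states no figure on this point, so there is none to reproduce. The check sets the Table 3 rows side by side and runs hypothetical participants through them.

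**Rows of SAP 2.0 Table 3**

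| Outcome | Rows | Cigarette item | `quit_tobacco_inhale` | Contacts |
|---|---|---|---|---|
| Primary (anabasine, else CO) | 1 | `quit_smoke_again` | must be No | weeks 1, 2, 4, 8, month 6 |
| Continuous, NNAL-validated | 1 | `quit_smoke_again` | must be No | weeks 1, 2, 4, 8, month 6 |
| Grace period | 3 | `quit_smoke_again` (validated rows also `quit_smoke_n`) | No at two or more contacts | weeks 4, 8, month 6 |
| Up to 5 cigarettes | 3 | `quit_smoke_n` | absent | not listed |
| 7-day | 3 | `quit_smoke_again`, `quit_smoke_7days` | absent | month 6 |

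Five rows carry the item (1 + 1 + 3) and six do not (3 + 3).

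**Hypothetical participants.** All report no cigarettes at any contact. "Val." means the anabasine-validated version.

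| Case | Item is Yes at | Month-6 biomarker | Primary | Grace, self-report | Up-to-5, self-report | Up-to-5, val. | 7-day, self-report | 7-day, val. |
|---|---|---|---|---|---|---|---|---|
| A | all contacts | anabasine 20 ng/ml | fail | fail | pass | fail | pass | fail |
| B | all contacts | anabasine 1 ng/ml | fail | fail | pass | pass | pass | pass |
| C | week 4 only | anabasine 1 ng/ml | fail | pass | pass | pass | pass | pass |
| D | month 6 only | anabasine 1 ng/ml | fail | pass | pass | pass | pass | pass |
| E | all contacts | anabasine missing, CO below 10 ppm | fail | fail | pass | pass | pass | pass |

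In case E, I read the CO fallback as applying when a CO value exists. Section 6.1 and the NNAL rows say so, although the condition printed in the anabasine rows reads the other way.

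**Reading the table**

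- Every case fails the primary outcome, and every case passes both self-reported outcomes that omit the item. In those rows the conflict is certain.
- In the validated rows it depends on the biomarker. Case A shows validation doing its work. Case C shows its limit: one sample at month 6 need not reveal use reported only at an earlier contact, yet that use still fails the primary.
- Case E needs a missing anabasine value and a product that leaves CO below the cut-off.

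**The case against.** **The item's meaning is inferred from its name.** This stands. If it records non-cigarette tobacco, all six omissions are inconsistent. If it records a puff of a cigarette, leaving it out of an outcome that tolerates up to five cigarettes is coherent, and only the 7-day rows need attention. Under both readings, section 6.1 does not say what the primary code does.

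**Validation catches most of it.** Largely true for current use. Protocol 9.0 section 3.1 calls anabasine an alkaloid found in tobacco, so a current user with a urine result should usually fail. SAP Table 1 also records tobacco heating systems through the e-cigarette variables. What remains under `quit_tobacco_inhale` may therefore be mostly combusted and visible to CO. This narrows the problem in the validated rows. It does nothing for the self-reported rows or for use that ended before month 6.

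**A reader might infer that the 6-month and the 12- and 24-month primary outcomes define smoking differently.** The documents do not show this. SAP 2.0 sections 2.7 and 7 exclude the later outcomes, so no derivation exists to compare. On the wording alone, SAP 6.1 and the 12/24-month text in protocol 5.1 both refer to cigarettes.

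**A reader might also infer that the planned contrast of 19% against 12% would shrink noticeably under another definition, especially if controls, who are asked not to use ENDS, turn to other tobacco.** That needs a rate of such use, a split by arm, and the assumption that these participants pass validation. The documents supply none of the three.

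**Conclusion.** The point holds as an unexplained inconsistency in SAP 2.0. The primary outcome's text and code disagree on inhaled tobacco, and six of the eleven cessation rows leave out an item that the other five use. A participant can be a smoker on the primary outcome and abstinent on the up-to-5 and 7-day outcomes solely because of that item. This is certain for the self-reported rows. For the validated rows it is conditional on a month-6 biomarker below the cut-off.

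The 6-month primary outcome can be computed as coded, and the code is the stricter rule. The damage is to its description and to the comparability of the secondary outcomes. No effect on the relative risk should be claimed for validated outcomes, because the documents give no rate of non-cigarette tobacco use. No error is shown at 12 or 24 months. For the up-to-5 rows, the conclusion assumes that the item records something other than a puff of a cigarette.

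**What to change.** 1. Keep `quit_tobacco_inhale` in the primary code. It already stood in SAP 1.0, written when the analysing statistician was to be blinded. Dropping it would also restore agreement with the text, but it would loosen the primary outcome after unplanned interim analyses and after an allocation-aware team took over the analyses (SAP 2.0 section 7 and the appended note on changes).
2. State in SAP 6.1 and protocol 5.1 that abstinence means no cigarettes and no other inhaled tobacco, and define the item by giving its eCRF wording.
3. If the item records non-cigarette tobacco, require No in the three up-to-5 rows, and require No at month 6 in the three 7-day rows. If it records a puff of a cigarette, add it to the 7-day rows only.
4. Use the same definition when the 12- and 24-month 7-day primary outcome is coded.
5. Enter the change in SAP Table 4, noting that allocation was known.

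The cost is a few sentences and a few lines of code; the 6-month derivation already uses the item. Secondary abstinence rates will fall slightly. The month-6 item may also look back further than seven days, which would make the 7-day rows somewhat too strict; the definition should say so.
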